1.3.2 Preclinical Toxicology

In mice, the LD₅₀ was determined to be about 2000 mcg/kg (6000 mcg/m²) of body weight, which is higher than the 100 mcg/kg of body weight that was found to be lethal in some dogs (2000 mcg/m²) and monkeys (1200 mcg/m²) (66). However, mithramycin was found to be essentially non-toxic in dogs and monkeys when administered at a dose of 24-50 mcg/kg/day (480-1000 mcg/m² dog, 288-600 µcg/m² monkey) intravenously for 24 consecutive days (66). The most frequently encountered toxicities at higher doses were bleeding, anorexia, vomiting, elevated liver function tests, electrolyte abnormalities, bone marrow suppression and azotemia (66).

Our preclinical data (20) as well as those reported by Grohar et al (65), indicate that IP doses of 1-2 mg/kg/day 3 times a week for 3 weeks are well tolerated in mice. In the Grohar study (65), necropsy demonstrated that mice treated at this dose and schedule had mild hypoalbuminemia, slightly increased ALT/AST levels with some evidence of liver toxicity described as mild to moderate, and minimal thrombocytopenia.

1.3.2.1 Pharmacokinetics

Administration of tritium labeled mithramycin to monkeys showed a terminal half-life of 5 hours. The peak cerebrospinal fluid concentration: plasma ratio was 0.12 and reached after 1 ½ hours (67). Preliminary pharmacokinetic parameters of ¹²⁵I-plicamycin (mithramycin) in human plasma using a radioimmunoassay were described (68). Three patients were studied and received mithramycin at a dose ranging from 0.85 to 1.0 mg/m² IV over 2 hours. Drug elimination was biphasic, with a mean elimination half-life of 10.6 hours (±1.7), and a clearance rate of 11.1 ±0.4 mL/min/m².

Kennedy et al (52) administered tritiated mithramycin by IV or IP routes in mice at doses closely approximating 2 mg/kg. Blood, liver, and kidney mithramycin concentrations following IP administration were similar if not higher than these observed following IV dosing. Tissue levels two hours after administration ranged from ~335 – 425 nM compared to 90 nM in blood (Table 2). Assuming an elimination half-life of ~10h, tissue levels most likely exceeded 50-100 nM for >24h.

1.3.3 Clinical Studies in Adults

Mithramycin underwent broad clinical evaluation in solid tumors and leukemias in the 1960's and was found to have some activity against leukemias, lymphomas and carcinomas (68-72); however, patient numbers and standard methods of evaluating responses were limited (Appendix 1). In particular, mithramycin was found to have activity against testicular cancers. In one series of 305 patients with Stage III testicular cancer, 10% of patients achieved a complete response, and an additional 25% showed some evidence of tumor regression (66); many of these cases were durable responses in patients with widely metastatic disease. In addition, mithramycin exhibited activity against Ewing sarcoma; two of five patients with EWFT exhibited widespread regression of metastatic disease following mithramycin treatment, one of whom had a durable complete response (73). This impressive response rate may be due to the ability of mithramycin to inhibit expression of EWS-FLI fusion transcript (65). Whereas more than 1,500 patients were treated with mithramycin, very few (~5) patients with lung cancers and no patients with esophageal carcinomas or MPM received this drug. Furthermore, only a small number of patients with breast, ovarian, or GI malignancies were treated with mithramycin. No conclusions can be drawn regarding clinical activity of mithramycin in these malignancies due to the variability of infusion schedules and timing of treatment response assessments.

Initial clinical trials suggested that 50 mcg/kg/dose, administered daily times 5 was an optimal treatment regimen (68). However, Spear et al (74) observed that 70% of 58 patients receiving this dose and schedule of mithramycin experienced significant toxicity including anorexia, nausea and vomiting. As a result, the dose of drug used in most subsequent studies was 25 mcg/kg/day on various schedules. The recommended dose in the Pfizer package insert for adults is 25-30 mcg/kg administered intravenously over 6 hours every 7-10 days of a 28 day cycle. Systemic toxicities appeared to be dose-related, tending to occur at doses above 30 mcg/kg/dose (66).

In general, the most frequent toxicities observed were nausea, vomiting, elevated liver function tests, infusional fever, mucositis, bleeding tendencies, thrombocytopenia, electrolyte abnormalities, proteinuria and elevated BUN/creatinine (summarized in (66)). Unfortunately, there was no systematic investigation of these toxicities, and it is unclear what levels of supportive care

these patients received. For example, nausea and vomiting occurred quite frequently; however, in at least two reports, nausea was controlled with phenothiazines or other anti-emetics (43, 69, 75).

Hemorrhage was the most profound toxicity observed in patients receiving mithramycin. In early reports hemorrhage was attributed to thrombocytopenia, and accounted for 3 deaths in 84 patients (42). Subsequent studies revealed that bleeding was dose-related, occurring in 5.4% of 1150 patients treated at 30 mcg/kg/day or more (66). Bleeding tended to occur around Day 4 of treatment, which is atypical of chemotherapy-induced thrombocytopenia. In addition, it appears that platelet counts remained >20,000/mcL in most of the patients experiencing hemorrhage, suggesting that bleeding was due to underlying clotting factor deficiencies or dysregulation of coagulation pathways. In all the cases of hemorrhage reported in the literature, it is not clear if the patients were taking any anti-coagulation medications, what type of blood product support was provided, how effective the blood product support was in that era, or what specific clinical and laboratory abnormalities were seen prior to the hemorrhage. Therefore, the frequency and severity of hemorrhage from mithramycin administered in the current era are unknown. Nevertheless, hemorrhage must be considered a rare, but serious potential toxicity of mithramycin therapy.

Additional rare but significant side effects attributable mithramycin include toxic epidermal necrolysis (76, 77), and possible potentiation of anthracycline-mediated cardiotoxicity (78). The true incidences of these toxicities are unknown and are not discussed in the package insert from Pfizer, or the previously filed IND for mithramycin.

Mithramycin has also been used for the treatment of malignant hypercalcemia, with 45% of patients responding to a single dose of mithramycin in one study (79). However, the bisphosphonate, pamidronate, has replaced mithramycin in this setting. For similar reasons, mithramycin was investigated for the treatment of Paget's disease of bone and was found to have good activity in the management of this disease. In one report, 10/10 patients with Paget's disease reported improvements in pain, and an increase in overall activity with treatment (75).

1.3.4 Recent Experience with Mithramycin in Adult Oncology Patients at the NCI

1.3.4.1 12C0151 Phase II Trial

In the recent Phase II trial (12C0151) in TSB/CCR/NCI, 12 patients (10 males; 2 females; median age 51y; range 40-72y) with refractory thoracic malignancies (6 MPMs, 2 esophageal cancers, 2 lung cancers, 2 synovial sarcomas) received 6h mithramycin infusions q day x 7, every 28 days. Response rates following two cycles, pharmacokinetics, and systemic toxicities (Cycle 1) were evaluated. A total of 20 cycles were administered to 12 patients; all were evaluable for toxicities. No objective responses were observed in 7 patients who were evaluable for treatment responses. No myelosuppression, uncontrollable nausea or vomiting were observed. No patients experienced bleeding. The lack of these toxicities, which have been associated with mithramycin treatment (66) may be attributable at least in part to higher purity of the current drug relative to what had been used previously.

Eight patients experienced transient, asymptomatic dose-limiting transaminitis following 25 mcg/kg/infusions. This toxicity always occurred on Day 4 of the infusion. Percutaneous biopsies from three individuals revealed apoptotic hepatocellular death (Figure 7A). Four patients (2 with MPM) had no hepatotoxicity and tolerated dose escalation to 30 mcg/kg/infusion. Peak and steady state mithramycin levels were 20 and 8 nM, respectively, which were not different in patients with or without hepatotoxicity (Figure 7B).

To address additional genetic variants that may have contributed to these LFT elevations, we conducted additional genotyping analysis using the DMET Plus array. We excluded the patient who had liver involvement to avoid confounding the analysis. ABCB4 and ABCB11 genotypes retained their significant association with LFT elevation (P<0.040) in spite of an individual with Grade 4 LFT elevations who was included in this group (**Figure 9A-B**). Variants in three other genes were found to be associated with LFT elevations: rs1143670 in *PEPT2* (**Figure 9C-D**), rs12680 in *RALBP* (**Figure 9E-F**), and rs6774801 in *CYP8B1* (**Figure 9G-H**). Since *PEPT2* genotypes did not demonstrate a genotype dose effect (i.e., the patient with GG had greater ALT and AST than those carrying GA), association between LFT elevations and this genotype may be confounded by other factors. No relationship between *PEPT2* and mithramycin outcomes was apparent in the literature. *RALBP* rs12680 was strongly associated with LFT elevations (P=0.0040), which are related to hepatocellular necrosis (<https://livertox.nlm.nih.gov/Plicamycin.htm>). *RALBP* has previously been associated with promoting hepatic inflammation and LFT elevations in mice and regulates cellular accumulation of doxorubicin by a poorly-characterized non-ABC-transport mechanism. Mithramycin has a conjugated quinone- and semiquinone-rich structure that is similar in structure to doxorubicin, suggesting that *RALBP* may influence cellular accumulation of mithramycin. *CYP8B1* is involved in the synthesis of cholic acid and thereby influences the composition of the bile pool. Since ABCB4 and ABCB11 are both involved in bile efflux, it is likely that *CYP8B1* and these

transporters are involved in hepatocellular bile accumulation. Accordingly, the enrollment criteria of the clinical trial is now amended to include the following genotypes: RALBP rs12680 (GG), CYP8B1 rs6774801 (CC or CA), ABCB4 rs2302387 (CC), and ABCB11 rs4668115 (GG) (**Figure 9I-J**). Since RALBP and CYP8B1 variant genotypes are relatively rare (variant allele frequency = 13% and 36% respectively), the present genotyping criteria should not preclude accrual of patients with thoracic malignancies. Plasma mithramycin levels measured in the 12 patients enabled simulation of pharmacokinetics of mithramycin administered via 24h infusions (**Figure 10**). Based on these data, doses in the range of 25-200 mcg/kg are estimated to produce plasma levels mediating pronounced antitumor effects in preclinical murine xenograft experiments.

2 ELIGIBILITY ASSESSMENT AND ENROLLMENT FOR PHASE I AND PHASE II

2.1 ELIGIBILITY CRITERIA

2.1.1 Inclusion Criteria

- 2.1.1.1** Patients with measurable (per RECIST see Section **6.3.3.1**), inoperable, histologically confirmed non-small cell lung cancer (NSCLC), small cell lung cancer (SCLC), esophageal carcinomas, thymic neoplasms, germ cell tumors, malignant pleural mesotheliomas or chest wall sarcomas, as well as patients with gastric, colorectal, pancreas or renal cancers and sarcomas metastatic to thorax.
- 2.1.1.2** Histologic confirmation of disease in the Laboratory of Pathology, CCR, NCI, NIH.
- 2.1.1.3** Disease amenable to biopsy via percutaneous approach or other minimally invasive procedures such as thoracoscopy, bronchoscopy, laparoscopy, or GI endoscopy.
- 2.1.1.4** Age ≥ 18 .
- 2.1.1.5** ECOG status 0-2.
- 2.1.1.6** Patients must have had or refused first-line standard chemotherapy for their inoperable malignancies.
- 2.1.1.7** Patients must have had no chemotherapy, biologic therapy, or radiation therapy for their malignancy for at least 30 days prior to treatment. Patients may have received localized radiation therapy to non-target lesions provided that the radiotherapy is completed 14 days prior to commencing therapy, and the patient has recovered from any toxicity. At least 3 half-lives must have elapsed since monoclonal antibody treatment. At least 6 weeks must have elapsed between mitomycin C or nitrosourea treatment.
- 2.1.1.8** Patients must have adequate organ and marrow function as defined below:
- a) Hematologic and Coagulation Parameters
 - i. Peripheral ANC $\geq 1500/\text{mm}^3$
 - ii. Platelets $\geq 100,000/\text{mm}^3$ (transfusion independent)
 - iii. Hemoglobin ≥ 8 g/dL (PRBC transfusions permitted)
 - iv. PT/PTT within normal limits (patient may be eligible for trial if abnormality is deemed clinically insignificant and cleared for protocol therapy by Hematology Consult service)
 - b) Hepatic Function
 - i. Bilirubin (total) < 1.5 X upper limit of normal (ULN)
 - ii. ALT (SGPT) ≤ 3.0 X ULN
 - iii. Albumin > 2 g/dL
 - c) Renal Function
 - i. Creatinine within normal institutional limits or creatinine clearance ≥ 60 mL/min/1.73 m² for patients with creatinine levels above institutional normal.
 - ii. Normal ionized calcium, magnesium and phosphorus (can be on oral supplementation)

2.1.1.9 Cardiac Function: Left ventricular ejection fraction (EF) >40% by echocardiogram, MUGA, or cardiac MR.

2.1.1.10 Ability of subject to understand, and be willing to sign informed consent.

2.1.1.11 Female and male patients (and when relevant their partners) must be willing to practice birth control (including abstinence) during and for 2 months after treatment, if female of childbearing potential or male having sexual contact with a female of childbearing potential.

2.1.1.12 Patients must be willing to undergo 2 tumor biopsies.

2.1.2 Exclusion Criteria

2.1.2.1 Patients with unfavorable ABCB4, ABCB11, RALBP or CYP8B1 genotypes associated with mithramycin-mediated hepatotoxicity.

2.1.2.2 Clinically significant systemic illness (e.g. serious active infections or significant cardiac, pulmonary, hepatic or other organ dysfunction), that in the judgment of the PI would compromise the patient's ability to tolerate protocol therapy or significantly increase the risk of complications.

2.1.2.3 Patients with cerebral metastases.

2.1.2.4 Patients with any of the following pulmonary function abnormalities will be excluded: FEV₁ < 30% predicted; DLCO, < 30% predicted (post-bronchodilator); Oxygen saturation ≤ 92% on room air (per vital sign measurement). Arterial blood gas will be drawn if clinically indicated.

2.1.2.5 Patients with evidence of active bleeding, intratumoral hemorrhage or history of bleeding diatheses, unless specifically occurring as an isolated incident during reversible chemotherapy-induced thrombocytopenia.

2.1.2.6 Patients on therapeutic anticoagulation. Note: Prophylactic anticoagulation (i.e. intraluminal heparin) for venous or arterial access devices is allowed.

2.1.2.7 Patients who are concurrently receiving or requiring any of the following agents, which may increase the risk for mithramycin related toxicities, such as hemorrhage:

- Thrombolytic agents
- Aspirin or salicylate-containing products, which may increase risk of hemorrhage
- Dextran
- Dipyridamole
- Sulfinpyrazone
- Valproic acid
- Clopidogrel

2.1.2.8 Lactating or pregnant females (due to risk to fetus or newborn, and lack of testing for excretion in breast milk).

2.1.2.9 Patients with history of HIV, HBV or HCV due to potentially increased risk of mithramycin toxicity in this population.

2.1.2.10 Hypersensitivity to mithramycin.

2.1.2.11 Patients who in the opinion of the investigator may not be able to comply with the safety monitoring requirements of the study.

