- Patients with measurable inoperable, histologically confirmed lung and esophageal carcinomas, thymic neoplasms, germ cell tumors, malignant pleural mesotheliomas or chest wall sarcomas, as well as patients with gastric, colorectal or renal cancers and sarcomas metastatic to the thorax are eligible.
- Patients with favorable germline SNPs in ABCB4, ABCB11, RALBP or CYP8B1 that are associated with resistance to mithramycin-induced hepatotoxicity.
- Patients must have had or refused first-line standard therapy for their malignancies.
- Patients must be 18 years or older with an ECOG performance status of 0–2, without evidence of unstable or decompensated myocardial disease. Patients must have adequate pulmonary reserve evidenced by FEV1 and DLCO equal to or greater than 30% predicted; Oxygen saturation $\geq 92\%$ on room air. ABG will be drawn if clinically indicated.
- Patients must have a platelet count greater than or equal to 100,000, an ANC equal to or greater than 1500 without transfusion or cytokine support, a normal PT/PTT, and adequate hepatic function as evidenced by a total bilirubin of <1.5 X upper limits of normal (ULN) and AST/ALT ≤ 3 X ULN. Serum creatinine within normal institutional limits or creatinine clearance ≥ 60 mL/min/1.73 m² for patients with creatinine levels above institutional normal.

Design:

- Single arm Phase I dose escalation to define pharmacokinetics, toxicities and MTD.

- Patient cohorts will receive 24h infusions of mithramycin targeting total doses previously administered during 7 daily six hour infusions at 30-50 mcg/kg.
- The 24h infusions will be administered every 14 days (1 cycle). Four cycles will constitute one course of therapy.
- Pharmacokinetics and toxicity assessment to define MTD will be assessed during Cycle 1 of the first course of therapy.
- Due to uncertainties regarding potential cumulative toxicities, no intra-patient dose escalation will be allowed.
- Once MTD has been defined, patients will be enrolled into two cohorts (primary thoracic malignancy vs neoplasm of non-thoracic origin metastatic to the chest) to determine clinical response rates at the MTD, using a Simon Optimal Two Stage Design for Phase II Clinical Trials targeting an objective response rate (RECIST) of 30%.
- Following each course of therapy, patients will undergo restaging studies. Patients exhibiting objective response to therapy or stable disease by RECIST criteria will be offered an additional course of therapy.

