11.4.1.6 Central Line

IV drugs on this study will be given through a central line, a “tunneled” catheter surgically inserted into one of the main blood vessels leading to the heart. The risks associated with the procedure include pain, bleeding, infection, puncture of the underlying lung and pulmonary embolism. Lung puncture can result in lung collapse, which might require that a chest tube be placed into the chest cavity (usually for a day or two) to help the lung re-expand. The long-term risks of the catheter include infection and clotting of the vein in which the catheter sits which can break off and travel to the veins near the neck, face, chest, arms or lungs (pulmonary embolism).

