12.1.6 Contraindications

The following medications are contraindicated:

- Anticoagulants, coumadin- or indandione-derivatives
- Heparin other than heparin flushes
- Thrombolytic agents
- Aspirin or salicylate-containing products, which may increase risk of hemorrhage
- Dextran
- Dipyridamole
- Sulfinpyrazone
- Valproic acid
- Clopidogrel

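### Section 12.1.6 contraindicates coumadin-type anticoagulants and non-flush heparin at any dose, but Section 2.1 excludes only therapeutic anticoagulation, so some patients on these drugs can meet the entry criteria

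*Combined protocol and SAP*

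**What the plan says.** Four parts of the protocol bear on anticoagulants.

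- **Exclusion 2.1.2.6:** "Patients on therapeutic anticoagulation. Note: Prophylactic anticoagulation (i.e. intraluminal heparin) for venous or arterial access devices is allowed".
- **Exclusion 2.1.2.7** bars "Patients who are concurrently receiving or requiring any of the following agents, which may increase the risk for mithramycin related toxicities, such as hemorrhage" and then lists seven agents. None is a coumadin-type drug or heparin.
- **Section 12.1.6** lists nine contraindicated agents. The first two are "Anticoagulants, coumadin- or indandione-derivatives" and "Heparin other than heparin flushes". Neither entry is limited to therapeutic dosing.
- **Inclusion 2.1.1.8(a)(iv)** requires "PT/PTT within normal limits (patient may be eligible for trial if abnormality is deemed clinically insignificant" and cleared by the Hematology Consult service). The précis asks for "a normal PT/PTT" and states no waiver.

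Section 4 covers blood products and filgrastim, antiemetics, antidiarrheals and electrolytes. It does not mention anticoagulants. Under Section 6.1.2.2, all concomitant medications go into the source documents, but C3D receives only routine baseline medications and those that cause an adverse event.

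**The concern.** The entry criteria and the contraindication list draw different lines around the same two drug classes. Staff who confirm eligibility against Section 2.1 alone could enroll a patient whose current drug is contraindicated later in the same document.

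The protocol itself gives reasons to care. Section 1.3.3 states: "Hemorrhage was the most profound toxicity observed in patients receiving mithramycin". Drug is given through a central line (Section 3.2) to hospitalized patients (Section 3.1), and Section 11.4.1.6 warns: "The long-term risks of the catheter include infection and clotting of the vein in which the catheter sits". The question of prophylaxis can therefore arise both at entry and during treatment.

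For the analysis, the stake is attribution. Under Section 3.1.1, a Grade 3 or greater nonhematologic toxicity counts as dose-limiting if it is even possibly related to treatment. In Section 3.1.2.1, one such event in three patients leads to up to three more at that level, and two close the level. A bleed in a patient on an anticoagulant is harder to attribute to mithramycin. Section 1.3.3 finds the same difficulty in the historical bleeding reports, where anticoagulant use was unclear.

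**Working it through.** No arithmetic applies beyond a count. The check sets the lists side by side and then asks which patients fall between them.

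**Step 1. Compare the lists.**

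| Agent in 12.1.6 | Listed in 2.1.2.7? | Other exclusion |
|---|---|---|
| Coumadin/indandione anticoagulants | No | 2.1.2.6, therapeutic use only |
| Heparin except flushes | No | 2.1.2.6, therapeutic use only |
| Thrombolytics | Yes | – |
| Aspirin/salicylates | Yes | – |
| Dextran | Yes | – |
| Dipyridamole | Yes | – |
| Sulfinpyrazone | Yes | – |
| Valproic acid | Yes | – |
| Clopidogrel | Yes | – |

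Seven of nine match, and 9 − 7 = 2 do not. The two are the anticoagulant entries. They have a criterion of their own in 2.1.2.6, so they were not simply left out. The mismatch comes from the qualifier *therapeutic*, which 12.1.6 does not use.

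**Step 2. Sort patients by what each section does.**

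| Patient | Section 2.1 | Section 12.1.6 | Agree? |
|---|---|---|---|
| Therapeutic heparin or coumadin-type drug | Excluded (2.1.2.6) | Contraindicated | Yes |
| Intraluminal line heparin only | Allowed (Note to 2.1.2.6) | Flushes excepted | Yes |
| Systemic prophylactic heparin or coumadin-type drug, PT/PTT abnormal and not cleared | Fails 2.1.1.8(a)(iv) | Contraindicated | Yes |
| Same drugs, PT/PTT normal or abnormality cleared | Can be met | Contraindicated | **No** |
| Systemic prophylaxis with another class | Not named | Not named | No conflict shown |

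Only the fourth row is a conflict.

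**Step 3. Look for another rule that closes the fourth row.** Section 4 has no prohibited list and no pointer to 12.1.6. PT/PTT is repeated before treatment (3.5.1), during it (3.5.2) and before biopsies (3.5.3), and Section 3.4 requires the eligibility laboratory parameters again before the next course. All of these are laboratory checks. None asks which drugs the patient takes or refers to 12.1.6.

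**Step 4. Check what the analysis database would hold.** An anticoagulant taken routinely at baseline reaches C3D. Section 6.1.2.2 keeps onetime, PRN and supportive medications out, so prophylaxis started during an admission could appear in the source documents only.

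**The case against.** The strongest reply is that the passages can be read together. The Note to 2.1.2.6 introduces intraluminal heparin with *i.e.*, which defines what is allowed and does not merely give an example. That allowance matches the flush exception in 12.1.6. Section 12.1.6 is also binding protocol text, and Section 9 monitoring covers protocol adherence and drug administration as well as eligibility. Much of this stands. A reader might infer that the protocol expressly permits systemic prophylaxis, or that meeting Section 2.1 authorizes treatment on a contraindicated drug. The documents support neither: 2.1.2.6 is silent on systemic prophylaxis, and 12.1.6 still applies.

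Second, PT/PTT must be normal. A reader might infer that every patient on prophylaxis passes Section 2.1. That does not follow, because a patient whose anticoagulant prolongs PT or PTT fails unless Hematology clears the result. This narrows the gap but does not close it, since a patient with a normal or cleared result still qualifies.

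Third, attribution is partly protected. Concurrent medications are on the screening calendar (Appendix 2), patients keep a medication log (Appendix 5), and Section 3.3 requires a full hematologic evaluation and Hematology consult for Grade 2–4 hemorrhage. This stands too. What remains is that C3D may lack an anticoagulant started on study.

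Fourth, Section 1.3.4.1 reports no bleeding among 12 patients over 20 cycles in the earlier NCI trial with the current drug. That is reassuring but small, and it says nothing about patients on anticoagulants.

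**Conclusion.** The inconsistency is real and limited. For the two classes named in 12.1.6, Section 2.1 can admit a patient on systemic prophylactic use when PT/PTT is normal or the abnormality is cleared, although 12.1.6 contraindicates the drug. Section 4 does not repair this for drugs started on study.

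The number of patients affected is unknown. The documents do not say how many receive prophylaxis or how often PT/PTT would be normal or cleared, so any share from none upward is compatible with them. The 5.4% of 1150 patients with bleeding in Section 1.3.3 is a historical figure at 30 mcg/kg/day or more and cannot be used to size the gap. It would also be too strong to extend the conflict to every anticoagulant, because 12.1.6 names only two classes.

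The conclusion assumes that *therapeutic* in 2.1.2.6 is meant to be distinct from prophylactic, as its own Note implies, and that intraluminal heparin corresponds to flushes. No sample size, error rate or response decision rule is affected. Correction is worthwhile because the toxicity concerned is the one the protocol ranks as most profound.

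**What to change.** 1. Reconcile 2.1.2.6, 2.1.2.7 and 12.1.6 so that one list governs both entry and on-study use, and state how systemic prophylactic use of the two classes is handled. Which rule applies is for the sponsor's clinicians to decide.
2. Cite that list in Section 4.
3. Add to Section 6.1.2.2 that anticoagulant use at the onset of each hemorrhage event is captured in C3D, including drugs that would otherwise be left out as onetime, PRN or supportive.

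The cost is wording in one amendment and one data field. Depending on the rule chosen, some patients may need a medication review before entry or may become ineligible; the documents give no basis for a number.
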